## INTERNATIONAL CLASSIFICATION OF FUNCTION, DISABILITY AND HEALTH (ICF)

In COMPASSgoal, we will consider function and disability, as well as activity and participation (including employment), based upon the widely-used International Classification of Function, Disability, and Health (ICF) framework developed under the auspices of the World Health Organization. Through this inclusive approach, we will best be able to document the natural process of recovery in TBI, including the occurrence of accelerated recovery, thereby addressing the needs of people with chronic TBI and providing potential benefit. At each assessment time point, participants (and their families and/or caregivers, if appropriate) will complete validated, standardized scales that capture outcomes in four central domains as defined by the ICF model: function, health, participation, and employment. The ICF presents an interaction of several basic concepts in disability that is widely used as a methodological tool for studying physical disability in general and TBI in particular. Relevant to the present project's conceptual integration is the ICF proposed model of contextual (personal and environmental) factors as they relate to the individual health condition.

## OPERATIONAL DEFINITION OF EXECUTIVE FUNCTIONING

*The operational definition of executive dysfunction/ inclusion into the study is based on both clinical diagnosis by a study physician and a standardized executive dysfunction measure, the FrSBe score, such that a total score or any of the 3 subscale scores < 1 SD compared to the normative score would indicate executive dysfunction sufficient to include in the study.*

**SIGNIFICANCE.** Studies emphasize the dramatic impact of neurological injuries among OEF/OIF active duty troops, as well as difficulties that such impairments present for returning service members. An understanding of the neurological disabling impact on executive function is necessary for both the accurate diagnosis of impairment and individual-tailoring of rehabilitation processes aimed at recovery of independent function.

**Significance and Alignment with RR&D Priority Area:** The proposed study directly supports the RR&D main goal to maximize functional recovery in Veterans as well as such additional goals as:

Topic area 1: integrating the Veteran back into work and society (**Hypothesis 1**)

Topic area 2: developing research that has strong potential for translation into clinical practice (**Hypothesis 2**)

The proposed goal self-management intervention COMPASSgoal promises to be effective for service members and their families, as well as for the civilian population, by timely detection of impaired decision-making due to executive dysfunction, facilitation of clinical behavioral monitoring, and promotion of the effectiveness of

neurorehabilitation and psychosocial procedures aimed at restoration of independent functioning and further community re-integration.

## RESEARCH DESIGN AND METHODS

### ***Overall Study Design***

The proposed 3-year multi-phase study will test two inter-related hypotheses. Hypothesis 1 is explored through a randomized controlled trial (RCT) testing the efficacy of a newly developed intervention COMPASSgoal in 110 young to middle aged Veterans with mild TBI assigned to intervention goal self-management or supported discharge groups. Hypothesis 2 is aimed at studying the multilevel relationships between four set of variables (neurological, psychological, behavioral, and social) measured repeatedly for the duration of the project. Assessments for the Veterans with mTBI involved with the project will be performed at baseline (pre-intervention for the COMPASSgoal group), 2 months after enrollment (or post-intervention for the COMPASSgoal group), and 3 months post-intervention/follow up.

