### **Power and sample size calculation**

110 participants with executive dysfunction due to diagnosed TBI will be randomized into the COMPASSgoal intervention or supported discharge groups, as assessed via the VHA TBI Comprehensive Evaluation screening tool. Participants in the supported discharge group will not receive the intervention, but will receive usual care provided by case managers with increased intensity of communication prompts. Participants in the intervention group will receive 8 goal self-management sessions over a period of approximately 10 weeks. We don't expect a significant change from post-intervention to 3 month post-intervention, the sample size calculations are based on a t-test for comparisons of mean change in the Community Reintegration of Service members (CRIS) subscale from pre- to post-intervention between two groups.

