## COMPASS PROCEDURES AND IMPLEMENTATIONS

Study procedures will take place at the DC VAMC in Washington, DC either face-to-face or over the VA Telehealth System (see Study Algorithm, Figure 5). All research procedures, including assessments, may be completed over the phone, not including informed consent. Over the 3-year course of the COMPASSgoal project, we will screen, consent, and baseline 110 Veterans, aged 18-55 years, who have been diagnosed with MTBI. All participating Veterans will undergo a battery of tests measuring executive function, real-world performance, TBI self-efficacy, emotional status and PTSD resilience, community integration, and quality of life. Each will receive additional screening of TBI and executive dysfunction to determine intervention eligibility. COMPASSgoal investigators will discuss each participating Veteran with his/her VA case manager.

Subsequently, Veterans will be randomized to intervention and control groups. The former will receive the COMPASSgoal self-management intervention developed to support vulnerable transitions identified during the first 6 months of the project. The latter will receive focused, but standard-of-care, support from the VA TBI Clinic team. Intervention group Veterans will receive 8, weekly, up to 90-minutes, one-on-one goal management sessions over a period of 2 months. Goal sessions with coaches, as well as control group interactions and assessments, will be audio recorded to better inform the researchers about the effectiveness of the interventions. These sessions may occur in person or over the phone. Veterans in both the intervention and control groups will receive assessments pre-, post-, and 3 months following completion of the COMPASSgoal intervention or supported discharge process. Data will be modeled longitudinally and on multiple levels to identify vulnerable transitions and predictors of community integration/participation outcomes.

Findings will form the basis for clinical practice guidelines.

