### ***Screening for exclusion-inclusion criteria***

Potential participants will be approached at least three months after TBI for informed consent. The results of the **VHA TBI Comprehensive Evaluation electronic template** will be reviewed following IRB approved and HIPAA compliant data collection procedures. The first data collection will take place within the first 14 days after screening and enrollment into the project.

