## STUDY ASSESSMENT SCHEDULE

Assessments will be performed at baseline (termed as "pre-intervention" for the COMPASSgoal group), 2 months (or post-intervention for the intervention group), and 3 months follow up for both intervention and supported discharge groups. Participants involved with the COMPASSgoal intervention (see relevant section below) will receive 8 goal self-management sessions over a 2-month period. The data will include demographics, level of TBI severity as confirmed by duration of post-traumatic amnesia and alteration of consciousness based on the VHA TBI Comprehensive Evaluation screening tool, executive dysfunction, PTSD, resilience, emotional status, coping, TBI self-efficacy, real-world tasks, and community integration. Family members will be invited to participate and answer the family-report FrSBe assessment either in person or over the telephone after being contacted through an IRB-approved letter.

**Table 2: Multifactorial Executive Functioning, Psychological, Behavioral, and Community Integration Measures (for a detailed description see Appendix 1, *Assessment Schedule*)**  

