## STATISTICAL ANALYSIS PLAN

### Overview

For this project, we plan to collect three major types of data assessed at times 1-3 (baseline/pre-intervention, 2 months/post-intervention, and 3 months follow up): community integration parameters including educational attainment and employment, individual characteristics such as PTSD; TBI self-efficacy, emotional status, coping, performance of real-world tasks, resilience and life satisfaction, and neuropsychological parameters including overall cognitive and executive functioning. Though we have removed the physical function assessments from future data collection, previously collected data on physical function may still be used for data analysis and subsequent publication and presentation purposes. The primary outcome will be the change in the three major types of parameters from pre- to post-intervention. Depending upon the hypothesis being tested (see Specific Aims section), participants will be stratified according to level of executive functioning, severity of conditions secondary to TBI (PTSD, level of functioning, emotional status), or degree of societal participation. Dependent variables will include TBI-self-efficacy, community integration indices, educational or work attainment as defined by the ICF qualifiers, and life satisfaction. Both objective (e.g. executive performance) and subjective (e.g., perceived TBI self-efficacy) data will then be obtained based on repeated measures over the three-year period. Multiple regression models will be fitted to explore continuous primary and secondary outcomes differentiating between groups at each time point and changes at the intra-individual and inter-individual levels over time. For categorical outcomes (e.g., low/high executive performance, or work status such as unemployed/employed, part-time/full-time), unconditional logistic and/or multinomial regression models will be implemented.

The basic testing of the hypotheses will involve ANOVA test and repeated measures ANOVA test. Bonferroni adjustments will be made to account for multiple testing.

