### **Hypothesis 1: Outcome Variables Main Effects for Community Re-integration Factors**

This algorithm is based on the assumption that an interaction between the intervention group and control groups can be modeled as a fixed effect. An LMM will then be used to evaluate whether the intervention had an effect at any time point or whether the intervention influenced change (growth, trajectory) in the outcome over the course of the study. The following will be considered for the analytical strategy:

- ANOVA, Repeated-measures ANOVA as well as MANCOVA will be used to compare the effect of the COMPASSgoal intervention vs. supported discharge group determined via baseline assessment. ANOVA will be used to compare the change from pre- to post-intervention between the two groups. Furthermore, in order to analyze the main effect of the COMPASSgoal intervention over time, a two-way repeated measures parametric ANOVA, as well as a non-parametric repeated measures Friedman ANOVA, will be performed, using the baseline time point, levels of TBI self-efficacy, or real-world tasks performance as the dependent variables. The levels of the repeated measures factor correspond to the number of assessments: baseline (pre-intervention) and 2 months post-intervention. The between-groups factor will be the intervention group vs. the supported discharge group. MANCOVA analysis will focus on the contrast in TBI self-efficacy between the intervention and supported discharge groups while accounting for a specified covariate: level of executive impairment as defined by FrSBE. In the case of non-normal residuals, we will use a nonparametric repeated measures approach. In the case of missing data, an LMM, which uses a maximum likelihood estimate to correct for unequal number of measures per subject, will be employed.
- *We will use Linear mixed models to control for potential confounding variables and baseline values will be utilized as a covariate. These models will allow for the additional control of potential within subjects clusters. These clusters, though not part of the formal hypothesis testing but byproducts of these models, will allow for conceptualization of additional future hypotheses.*

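### T2, the only powered time point, has no single definition; on one reading the arms could reach it after intervals differing by about -0.7 to +3.3 weeks

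*Combined protocol and SAP*

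**What the plan says.** T2 is described in five places, not all in the same way.

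- Overall Study Design: "2 months after enrollment (or post-intervention for the COMPASS" group.
- Study Assessment Schedule: "2 months (or post-intervention for the intervention group), and 3 months follow up for both intervention and supported discharge groups". The start of the 2 months is not given here.
- COMPASS Procedures and Implementations: "Veterans in both the intervention and control groups will receive assessments pre-, post-, and 3 months following completion of the" intervention or of the supported discharge process. Each arm is tied to its own process.
- SAP Overview: "baseline/pre-intervention, 2 months/post-intervention, and 3 months follow up", which treats 2 months and post-intervention as one time point.
- SAP Hypothesis 1: "baseline (pre-intervention) and 2 months post-intervention" as the levels of the repeated factor.

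The session period also varies. COMPASS Procedures and Implementations has "one-on-one goal management sessions over a period of 2 months", and the Study Summary and Study Assessment Schedule agree with it. Power and sample size calculation has "8 goal self-management sessions over a period of approximately 10 weeks". The Supported Discharge section gives controls a contact every two weeks over a fixed eight weeks.

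On the start of the clock, Screening for exclusion-inclusion criteria says "The first data collection will take place within the first 14 days after screening and enrollment into the project", whereas the Study Summary equates baseline with enrollment. Randomization follows baseline. I found no visit window, and no rule that dates T2 for a COMPASS participant who delays or stops sessions.

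**The concern.** The sample size rests on the between-arm difference in CRIS change from T1 to T2. That difference estimates the treatment effect cleanly only if both arms are measured after the same interval. If one arm's visit is triggered by finishing treatment and the other's by the calendar, any change in participation with time alone falls unequally on the arms.

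The second risk concerns who is measured. If T2 waits for the end of sessions, a COMPASS participant who delays or stops has no date on which to be seen, and T2 may be late or lost mainly in that arm. The Missing Data section itself anticipates that people with poorer treatment results may drop out, and rules out imputing missing outcomes. This risk does not depend on any drift in the CRIS score.

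**Working it through.** **The plan's own figure.** Inputs from Power and sample size calculation: standardized effect 0.71, SD 7, two-sided alpha 0.05, power 90%.

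- Normal approximation: n = 2 × (1.960 + 1.282)² / 0.71² = 41.7, so 42 per arm.
- The exact two-sample t-test needs 43 per arm at 0.71 and 44 at 0.70. Power at 44 per arm and 0.71 is 90.9%.
- Loss of 20%: 44 / 0.80 = 55 per arm, 110 in total.

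The stated 44 and 55 reproduce. Visit timing does not enter this calculation, so the sample size does not depend on the present point.

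**Baseline-to-T2 interval, enrollment-anchored controls.** Two months = 2 × 365.25 / 12 / 7 = 8.7 weeks. On this reading:

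- control interval = 8.7 - (lag from enrollment to baseline), with a lag of 0 to 2 weeks;
- COMPASS interval = session period, assuming that sessions start at baseline: 8 weeks (eight weekly sessions), 8.7 weeks (2 calendar months) or 10 weeks;
- gap = COMPASS interval - control interval.

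| Lag (weeks) | Control | COMPASS | Gap |
|---|---|---|---|
| 0 | 8.7 | 8.0 | -0.7 |
| 0 | 8.7 | 8.7 | 0.0 |
| 0 | 8.7 | 10.0 | +1.3 |
| 2 | 6.7 | 8.0 | +1.3 |
| 2 | 6.7 | 8.7 | +2.0 |
| 2 | 6.7 | 10.0 | +3.3 |

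**Completion anchor in both arms.** With controls at a fixed 8 weeks and no lag, the gap is 8 - 8 = 0, 8.7 - 8 = +0.7 or 10 - 8 = +2.0 weeks. A parallel completion rule therefore does not equalize the intervals if the sessions take about 10 weeks.

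**Common calendar visit.** If both arms are seen at 2 months from one starting point, the gap is zero and COMPASS non-completers have a date like everyone else.

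Sessions that slip beyond the stated period would widen the gap further on either of the first two readings.

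**From weeks to points.** With untreated drift of r CRIS points per week, the bias is r × gap. The planned difference is 0.71 × 7 = 4.97 points. The documents give no value for r, so the calculation stops at weeks.

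**The case against.** The best reply is that the bracket is only a label. In Overall Study Design it parallels the preceding bracket, which gives baseline its COMPASS name, and the Study Assessment Schedule says outright that the baseline name is just a term. The SAP Overview puts 2 months and post-intervention either side of a slash. The control contact period was built to correspond to the intervention arm. On this view T2 is one nominal 2-month visit for everybody. The reading is fair, and it is why the gap can be zero. It does not settle the matter, because no section states a common calendar date for both arms, and about 10 weeks of sessions does not fit a 2-month visit held after the last session.

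The 14-day lag is also open to challenge. It arises before randomization and so affects both arms alike. It separates them only if controls are timed from enrollment and COMPASS from sessions, and the Study Summary equates baseline with enrollment. The +3.3 weeks is therefore a stacked worst case.

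The SAP Hypothesis 1 wording is weak evidence of a further definition. It may be the Overview phrase with the slash lost, and I leave it out of the range.

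The mixed models use all available data, so one missed visit need not remove a participant, and the follow-up letters make no distinction by arm. Both points reduce the cost of a lost T2. Neither corrects unequal timing or supplies a missing date.

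**Conclusion.** T2 is defined inconsistently, and the inconsistency touches the only powered contrast. If COMPASS T2 follows the end of sessions, the baseline-to-T2 interval may differ between arms by about -0.7 to +3.3 weeks. The range rests on sessions starting at baseline and on the stated session periods and lag. On the same reading, COMPASS participants who delay or stop sessions have no T2 date, so outcomes could be late or missing mainly in that arm, with no imputation to follow.

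A reader might infer more, and the documents do not support it:

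- That the arms *will* be measured after different intervals. This is one reading; a shared 2-month visit is another.
- That a control always has a T2 date. The procedures section ties control assessments to completion of a process too, although that process runs by the calendar.
- That the error passes to T3 because T3 is counted from T2. The text counts T3 from the end of the intervention or of each arm's process.
- That the bias is a given share of the planned 4.97 points. This needs a drift rate that the plan does not state, and the power section expects no significant change between post-intervention and the 3-month follow-up.

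**What to change.** In Overall Study Design, COMPASS Procedures and Implementations, Study Assessment Schedule, SAP Overview and SAP Hypothesis 1, use one definition: T2 falls a stated number of weeks after randomization, within the same window in both arms, and is done regardless of how many sessions were completed. Define T3 from the same anchor in both arms. Record actual visit dates, so that the achieved intervals can be reported by arm.

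Before the target is set, the sponsor must reconcile the session-period statements in the Study Summary, Power and sample size calculation, COMPASS Procedures and Implementations, and Study Assessment Schedule, so that the T2 target fits the period chosen. The Study Summary's equation of baseline with enrollment should be aligned with the 14-day allowance.

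The cost is protocol and SAP wording plus a visit-window rule; the sample size stays as it is. One small downside is that some COMPASS participants may reach T2 before their last session, so the estimate is of the effect at a fixed time after allocation and not strictly after a completed course.

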### ***Overall Study Population***

*One hundred and ten Veterans with residual deficits in executive function due to mild TBI will be recruited from the TBI clinics at the DC VAMC over the three-year period of the study. Severity of TBI will be determined by the DC VAMC attending clinician using the VHA TBI Comprehensive Evaluation electronic template. The Frontal Systems Rating Scale (FrSBe) will be used to identify individuals with differing levels of executive dysfunction. The operational definition of executive dysfunction/ inclusion into the study is based on both clinical diagnosis by a study physician and a standardized executive dysfunction measure, the FrSBe score, such that a total score or any of the 3 subscale scores < 1 SD compared to the normative score would indicate executive dysfunction sufficient to include in the study.* Prior history of known bipolar disorder, schizophrenia or severe psychiatric illness will be determined first by review of the medical history. If the potential participant's medical record has no documentation of mental health evaluation within the year prior to enrollment, the M.I.N.I. Neuropsychiatric Interview will be administered for exclusionary screening purposes..

We will make every effort to balance the sample by age, gender, and education following the study inclusion-exclusion criteria. Based on previous studies conducted with the VA population in the Greater Washington Area, we expect that approximately 10% of the study participants will be female, and 70% will be African-American. The total number of study participants (N = 110) accounts for a 20% attrition rate in a neurologically-disabled population due to their health condition and related problems.

### ***Inclusion-exclusion criteria***

One hundred and ten medically stable individuals with various levels of TBI severity who are not currently evaluated at weekly meetings by the Polytrauma Interdisciplinary team for TBI-related skilled therapy management will be enrolled into the study according to the following inclusion and exclusion criteria:

**Table 1. Study inclusion-exclusion criteria**

	Inclusion Criteria	Exclusion Criteria
COMPASS: community re- integration study	TBI of at least mild severity using criteria related to disturbance of consciousness (VHA TBI Comprehensive Evaluation screening tool)	Unable to provide informed consent and no proxy available
	Obtained informed consent	Severe impairment of language or day-to-day memory that would preclude participation in a verbally-based therapy
	Males or females of working age, between the ages of 18 and 55	Life expectancy of less than 36 months

Medically stable with physician approval to participate	Severe multiple trauma (as judged by the attending physicians and/or investigators that is too severe to participate in this study) such as severe burns, serious organ damage, amputations, multiple fractures.
Ability to comprehend and communicate in English at a 6 th grade level	History of substance abuse severe enough to cause neurologic damage, pre-morbid history of neurologic disease (e.g., stroke)
Executive dysfunction as identified by Frontal Systems Rating Scale (FrSBe) and/or other study assessments (see Table 2)	Prior history of known bipolar disorder or schizophrenia or severe psychiatric illness as determined by clinical judgment and the medical record. The MINI assessment will be administered if no clinical judgment is on record within year prior to enrollment.

